03	Added summary of changes, increased number of subjects, number of sites and study duration/completion milestones. Updated primary safety endpoint and hypothesis, added >65 enrollment goal, added HCP experience questionnaire, made visit windows more clear, added patient call between visits for AE documentation, removed same pocket reinsertions, added DSMB and CEC to AE section, added Skin thinning to AE list, updated sample size justification, updated visit schedule table (format, visit windows, protocol
04	added patient call at 14 days after insertions for AE documentation
05	Updated physician and HCP to HCP (physicians, physician assistants, and/or nurse practitioners).
06	Updated section 8.3 to include a statement for 30% of insertions/removals performed by NPs and PAs
07	Updated abbreviations and exclusion criteria to remove MRI.

Senseonics, Inc. Protocol #: CTP-0034, Version 10

2023

Confidential Information

Page 2 of 43 Effective Date:#: 20 March

08	Update to transition study subjects to the 180-day Eversense E3 CGM System. Updated primary safety endpoint sample size justification (section 8.4) to adjust for a combination of the 90-day and 180-day sensor insertion and removal cycles to achieve at least 1400 Sensor wear cycles. Updated the clinical study background including addition of the PROMISE study and FDA approval of the Eversense E3 CGM System, and removal of OUS feasibility studies. Study visit window was updated from + 0 – 7 days to ±7 days. Expected date to complete follow-up of all study participants updated from 48 months to 60 months.
09	Changing participation from 24 to 27 months of CGM use, and adding, or until at least 1400 cycles of Sensor use are achieved.

Confidential Information

10	Changing Other Safety Endpoints to "up to 27 months" from "through 24 months." Clarified sections 8.4.3 and 10, that subjects will be encouraged to remain in the study up to 27 months. Updated section 6.9 (Residual DXA testing) to indicate, as applicable, that Sensors will be removed at 24 or 27 months. Clarified statement in Section 10 that follow-up for all study subjects will be complete up to 27 months (from 24 months), or after at least 1400 sensor cycles are completed study wide, after study enrollment is complete.
----	--

Collidering

Confidential Information

SYNOPSIS

Study Aspect	Description
Title:	A Post Approval Study to Evaluate the Long-term Safety and Effectiveness of the Eversense® Continuous Glucose Monitoring (CGM) System
Purpose:	To evaluate the long-term safety and effectiveness of the Eversense CGM System over repeat insertion and removal cycles
Primary Safety Objective:	To demonstrate the long-term safety of the Eversense CGM System
Primary Safety Endpoint:	Incidence of the composite of infection, secondary procedures to remove the Sensor, or procedure-related adverse events of at least moderate severity
Other Safety Endpoints and Analyses:	Rate of all device-related and insertion and removal procedure-related adverse events
	Rate of device breakage
	 Rate of device-related and insertion and removal procedure- related serious adverse events up to 27 months post-first Sensor insertion
	 Subgroup analysis of all safety endpoints based on: Age (<65 years vs. ≥65 years, minimum 40 subjects)
Effectiveness Objective:	To demonstrate the long-term effectiveness of the Eversense CGM System
Primary Effectiveness Endpoint:	Time in range, defined as glucose values between 70 mg/dL and 180 mg/dL, at 12 months compared to the first month post-first Sensor insertion
Effectiveness Endpoints:	Average hours of use per day
	Change in HbA1c levels at each 6-month interval
Patient Perspective Endpoint:	Patient satisfaction with CGM system use

Senseonics, Inc. Protocol #: CTP-0034, Version 10

2023

Confidential Information

Effective Date:#: 20 March

Page 5 of 43

Other Endpoints:	 Success rate of insertion and removal procedures, overall and by HCP experience (learning curve by number of cases), to evaluate training program Rate of serious adverse events based on HCP experience with the insertion and removal of Sensors (learning curve by number of cases) HCP feedback questionnaire regarding insertion/removal
Study Duration:	Study Enrollment: Approximately 36 months Patient Participation: - Approximately 27months
	Tationer articipation. Approximately 27 months
Subject Follow-up:	Patients will return to the clinic at approximately 3-month or 6-month intervals for exchange of the Sensor and for routine follow up of their diabetes. Patients will participate for up to 27 months of CGM system use or until at least 1400 cycles of Sensor use are achieved.
Design:	Prospective, multi-center study at up to 30 sites in the U.S. enrolling up to 400 adult subjects with diabetes (to insert 273 subjects) including at least 40 subjects ≥65 years to achieve at least 1400 Sensor cycles. The subjects will have one Sensor inserted by trained health care professionals approximately every 3 to 6 months dependent upon the Sensor used (90-day Eversense Sensor or 180-day Eversense E3 Sensor).
Statistical Analysis and Study Reporting:	Statistical analysis with interim reports will be initiated per FDA PAS guidelines of every 6 months for the first 2 years and annually thereafter. Study hypotheses will be evaluated at end of study

Page 6 of 43

Effective Date:#: 20 March

ABBREVIATIONS

AE Adverse Event
BG Blood Glucose
BMI Body Mass Index

CGM Continuous Glucose Monitoring System

CFR Code of Federal Regulations

Case Report Form CRF DCF **Data Clarification Form Diabetic Keto-Acidosis** DKA **DMS Data Management System DQMP** Data Quality Management Plan eCRF electronic Case Report Form **EDC Electronic Data Capture** ΕN **European Standard** EU **European Union**

FDA Food and Drug Administration

HbA1c Hemoglobin A1c

HCP Health Care Providers (physicians, physician assistants, and/or nurse practitioners)

HHD Hand Held Device

HPA Axis Hypothalamic-Pituitary-Adrenal axis

IRB Institutional Review Board

ISO International Organization for Standardization

ISPAD International Society for Pediatric and Adolescent Diabetes

ITT Intention-to-treat
MMA Mobile Medical App
PAS Post-Approval Study
PMA Premarket Approval

PP Per Protocol
RF Radio Frequency

SAP Statistical Analysis Plan
SAE Serious Adverse Event

SMBG Self-Monitoring Blood Glucose

UADE Unanticipated Adverse Device Effect

Senseonics, Inc. Confidential Information Page 7 of 43
Protocol #: CTP-0034, Version 10 Effective Date:#: 20 March

O TABLE OF CONTENTS

1. IN	TRODUCTION, IDENTIFICATION OF THE DEVICE, AND RATIONA	LE12
1.1.	Names, Intended Use, and Description of Study Device	12
1.1.	1. Description	13
1.1.	2. Calibration	14
1.2.	Summary of Pre-clinical and Clinical Experience	15
2. Pu	rpose of this study	15
3. ST	UDY OBJECTIVES, ENDPOINTS AND HYPOTHESES	15
3.1.	Primary Safety Objective	15
3.2.	Primary Safety Endpoint	16
3.3.	Primary Safety Hypothesis	16
3.4.	Other Safety Endpoints	
3.5.	Effectiveness Objective	16
3.6.	Primary Effectiveness Endpoint	17
3.7.	Other Effectiveness Endpoints	17
3.8.	Patient Perspective Endpoint	17
3.9.	HCP Perspective Endpoint	17

1. INTRODUCTION, IDENTIFICATION OF THE DEVICE, AND RATIONALE

Despite recent improvement in therapies, diabetes mellitus continues to be a difficult medical condition to treat. The challenge remains to achieve desired glycemic control and to prevent both the short-term consequences (severe hypoglycemia and DKA) and long-term complications (retinopathy, neuropathy, nephropathy, and cardiovascular problems). The monitoring of blood glucose by the patient with diabetes is one of the key tools of diabetes self-care. The current standard glucose monitoring regimen for patients with diabetes involves using a small portable meter to obtain a capillary fingertip glucose measurement multiple times a day. According to the International Society of Pediatric and Adolescent Diabetes (ISPAD), "successful application of intensified diabetes management with multiple injection therapy or insulin infusion therapy requires frequent self-monitoring of blood glucose (four to six times a day) and regular, frequent review of the results to identify patterns requiring adjustment to the diabetes treatment plan." i Despite this diagnostic procedure and therapeutic interventions, due to the nature of diabetes, glucose values may fluctuate widely throughout the day. In addition, as the BG meter value shows only a point in time glucose level, even patients who monitor frequently, may miss significant hypoglycemic and hyperglycemic excursions. Continuous glucose monitoring (CGM), which measures interstitial glucose levels, has been developed recently and has been shown to be associated with improved glycemic control in adults with type 1 diabetes. Current commercially available CGM devices require the repeated, frequent insertion of a Sensor by the patient.

Senseonics, Inc. a medical device manufacturer headquartered in Germantown, Maryland, USA, is developing a new CGM System intended for measuring interstitial fluid glucose levels in adults with diabetes mellitus. The Eversense CGM System measures glucose levels every 5 minutes using Sensors implanted under the skin by a trained clinician. Unlike commercially available transcutaneous continuous glucose monitoring devices with short operating lives (up to 14 days), the Sensor is intended to be inserted subcutaneously with no Sensor part protruding from the skin, and the operating life is intended to be up to 90 days (for the Eversense Sensor) or 180 days (for the Eversense E3 Sensor) or until Sensor end-of-life indicator is reached.

1.1. NAMES, INTENDED USE, AND DESCRIPTION OF STUDY DEVICE

The study devices are the Eversense Continuous Glucose Monitoring System ("Eversense CGM System"), which is the 90-day system, and the "Eversense E3 CGM System", which is the 180-day system. The description below is accurate for both CGM systems.

The Eversense Continuous Glucose Monitoring System is a glucose monitoring device intended to continually measure interstitial fluid glucose levels in individuals with diabetes for the operating life of the Sensor. The Eversense Continuous Glucose Monitoring System is intended to be used:

- To provide real-time glucose readings directly to the user
- To provide glucose trend information

[figure not shown]
Senseonics, Inc. Confidential Information Page 12 of 43

Protocol #: CTP-0034, Version 10 Effective Date:#: 20 March

• To provide alerts for the detection and prediction of episodes of low blood glucose (hypoglycemia) and high blood glucose (hyperglycemia).

The Eversense CGM System consists of:

- 1. Glucose Sensor, (approximately 3.5 mm [0.138"] diameter x 18.3 mm [0.720"] length) which has a ring that elutes the steroid dexamethasone.
- 2. Battery-powered external Transmitter ("Transmitter")
- 3. Mobile Medical Application (MMA) for display of glucose information that runs on a Handheld Device (HHD).

Accessories to the system include:

- 1. Blunt dissector for creating a pocket under the skin
- 2. Insertion tool used to place the Sensor into the pocket.
- 3. Transmitter accessories (power supply, adhesive patches)

1.1.1. DESCRIPTION

The Eversense CGM Sensor uses a selective, fully reversible binding between glucose and a unique fluorescent indicator macromolecule that is grafted on the surface of the Sensor. The fundamental recognition reaction is a reversible condensation of the cis-diol groups of glucose with the bis-boronate moiety of the indicator macromolecule. Glucose binding by the indicator macromolecule results in an increase in fluorescence intensity. Glucose signal transduction is accomplished by measuring the fluorescence intensity modulation using the Sensor's optical system.

Senseonics, Inc.
Protocol #: CTP-0034, Version 10

Confidential Information

Page 13 of 43 Effective Date:#: 20 March

The Eversense System Transmitter powers the Sensor and receives signals from the Sensor across the skin. The Sensor does not contain a battery or other stored power source; instead, it is powered discretely, as needed, by a simple inductive magnetic link between the Transmitter and Sensor. Signals carrying glucose concentration data are superimposed upon the magnetic power link between the two components. This results in "passive" telemetry, rather than an "active" radio frequency (RF) transmission, between the Sensor and Transmitter. Between readings, the Sensor remains electrically dormant and fully powered down. At each query (automatically set for approximately every five minutes, with a duration of approximately 100 milliseconds), the Transmitter sends power (via magnetic link) to activate the Sensor, and then uses this same magnetic link to capture the reading. Finally, the Transmitter calculates and stores the measured glucose value for transmission to the Mobile Medical Application.

Components of the Eversense CGM System are traced by serial number and/or lot number. The Sensor, Sensor holder, insertion tool, and blunt dissector are provided sterile. Sterilized components also have an expiration date. The device is labeled in compliance with regulatory language requirements. The Instructions for Use are provided with each shipment. Transmitters will be provided for single-subject use in this clinical trial.

Insertion of the Sensor is a minimally invasive procedure and clinical investigators representing the intended use population (Endocrinologists, Internists, General and Family Practitioners, including physicians, physician assistants, and/or nurse practitioners) will be appropriately trained in the procedure prior to insertion or removal of the Sensor. Training and qualifications of investigators will be documented per the formal commercial training procedure.

1.1.2. CALIBRATION

The Eversense CGM System will be calibrated by the Subjects according to the Eversense CGM User Guide, using their blood glucose meter (BG meter). The calibration process automatically moves through three phases: Warm Up, Initialization, and Daily Calibration:

- Warm Up is the first 24 hours after Sensor insertion. During this period, Glucose information is not calculated. No calibration is performed.
- Initialization can be performed a minimum of 24 hours after Sensor insertion. Following the Warm-up phase, the entering of four successful calibration BG readings within 24 hours is required for successful completion of Initialization. Glucose information will begin to be calculated after the second calibration is entered successfully.
- Daily Calibration requires 2 successful calibrations per day*, a minimum of 10 and maximum of 14 hours apart.

Senseonics, Inc. Confidential Information Page 14 of 43
Protocol #: CTP-0034, Version 10 Effective Date:#: 20 March

* The Eversense E3 CGM System transitions on day 21 to requiring a combination of 1 or 2 calibrations per day depending upon the preset rules in the firmware (the device will prompt calibration 12 or 24 hours after the prior calibration timepoint).

If the patient does not wear the Transmitter for more than 24 hours, or is unable to enter a successful calibration, then glucose information will not be calculated, and the patient will reenter the Initialization phase.

1.2. SUMMARY OF PRE-CLINICAL AND CLINICAL EXPERIENCE

Bench testing and animal testing have been conducted on the Senseonics (Eversense) CGM System to characterize performance, evaluate biocompatibility and demonstrate proof of principle in primates.

Four major pivotal safety and efficacy studies have been completed and submitted for regulatory approval. The European pivotal study, PRECISE was completed in August 2015 and Senseonics received CE Mark in May 2016; two U.S. pivotal studies (PRECISE II, completed in July 2016 and PRECISION, completed in February 2018) were also completed and FDA approval was received in June 2018. Lastly, the U.S. pivotal study PROMISE was conducted to evaluate the safety and accuracy of the 180-day Eversense CGM System. The study was completed in May 2020 and formed the basis of FDA approval of the Eversense E3 CGM System (trade name of the 180-day system) in February 2022.

These studies demonstrated that the Senseonics (Eversense) CGM System provided reliable interstitial fluid glucose readings for periods of up to approximately 90 or 180 days (depending on the study) when compared to reference blood glucose analyzer measurements, with a favorable safety profile.

2. PURPOSE OF THIS STUDY

The purpose of this post-approval study (PAS) is to provide long-term safety and effectiveness of the Eversense CGM System (PMA Application P160048) in the post-market setting. In the premarket setting, the PRECISE II and PRECISION studies demonstrated safety and accuracy of the CGM system in estimating blood glucose levels compared to reference blood glucose analyzer levels to 90 days. The PROMISE study demonstrated safety and accuracy of the CGM system up to 180 days. This PAS study will provide safety and effectiveness data up to 27 months of repeated use.

3. STUDY OBJECTIVES, ENDPOINTS AND HYPOTHESES

3.1. PRIMARY SAFETY OBJECTIVE

The primary safety objective is to demonstrate the long-term safety of the Eversense CGM System.

Senseonics, Inc.
Protocol #: CTP-0034, Version 10

Confidential Information

Page 15 of 43

2023

Effective Date:#: 20 March

3.2. PRIMARY SAFETY ENDPOINT

The primary safety endpoint is the incidence of the composite of infection, secondary procedures to remove the Sensor, or procedure-related adverse events of at least moderate severity.

3.3. PRIMARY SAFETY HYPOTHESIS

The primary safety composite endpoint will be evaluated in the following hypothesis test against a Performance Goal of 4%:

H₀: The rate of the composite of infection, secondary procedures to remove the Sensor, or procedure-related adverse events of at least moderate severity (p) is greater than or equal to 4%.

$$H_0$$
: p ≥ 4%

H₁: The rate of the composite of infection, secondary procedures to remove the Sensor, or procedure-related adverse events of at least moderate severity (p) is less than 4%.

$$H_1$$
: p < 4%

The rate will be tested against the Performance Goal of 4%, using an exact, binomial test, with a one-sided p-value of 0.05 considered evidence of statistical significance. Data will be analyzed on a per cycle basis.

3.4. OTHER SAFETY ENDPOINTS

Other safety endpoints include:

- Rate of all device-related and insertion and removal procedure-related adverse events (serious and non-serious events) up to 27 months post-first Sensor insertion
- Rate of device breakage up to 27 months post-first Sensor insertion
- Rate of device-related and insertion and removal procedure-related serious adverse events up to 27 months post-first Sensor insertion
- Subgroup analysis of safety endpoints based on:
 - Age (<65 years vs. >65 years, minimum 40 subjects)
 - Diabetes type (I vs. II)
- Race (non-Caucasian vs. Caucasian)

3.5. EFFECTIVENESS OBJECTIVE

Senseonics, Inc. Confidential Information Page 16 of 43
Protocol #: CTP-0034, Version 10 Effective Date:#: 20 March

The primary effectiveness objective is to demonstrate the long-term effectiveness of the Eversense CGM System.

3.6. PRIMARY EFFECTIVENESS ENDPOINT

The primary effectiveness endpoint is Time in Range, which is defined as glucose values between 70 mg/dL and 180 mg/dL, at 12 months post-first Sensor insertion compared to the first month post-first Sensor insertion.

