8.3. OTHER ENDPOINTS

Safety

Other safety endpoints will be summarized using descriptive statistics appropriate to the endpoint being evaluated. There are no formal hypotheses or tests for statistical significance associated with secondary endpoints.

The rates for serious and non-serious adverse events will be summarized as binomial proportions, together with the exact, one-sided upper 95% confidence bound. These will include insertion/removal procedure-related adverse events, and rate of device breakage.

Subgroup analysis of all safety endpoints based on:

- Age (<65 years vs. >65 years, minimum 40 subjects)
- Diabetes type (I vs. II)
- Race (non-Caucasian vs. Caucasian)

Effectiveness

Effectiveness will be measured as percentage change in the percent time in range (based on hours) at one month compared to 12 months using a time in range definition of glucose values between 70 mg/dL and 180 mg/dL. The Time in Range will be summarized as the mean of the subject percentages, together with the median, standard deviation, minimum, maximum, and 25th / 75th percentiles.

Summary statistics will also be provided for the change in HbA1c levels from baseline, and average hours of use per day.

Patient Perspective

Patient satisfaction as measured by validated questionnaires (CGM satisfaction survey and Diabetes Distress Scale) administered at select visits will be reported. The patient questionnaire scores will be summarized as means, median, standard deviation, minimum, maximum, and 25th / 75th percentiles.

Page 39 of 43

Effective Date:#: 20 March

Other Endpoints

Success rates for insertion and removal procedures will be presented to evaluate the

Senseonics, Inc. Confidential Information Protocol #: CTP-0034, Version 10

effectiveness of the training program. Success rate will also be presented based on the HCP experience with insertion and removing Sensors (learning curve by number of cases). It is anticipated that approximately 30% of the insertion and removal procedures will be done by nurse practitioners and physician assistants.

The rates of serious adverse events based on HCP experience with inserting and removing Sensors (learning curve by number of cases) will be examined.

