8.4.2. EFFECTIVENESS ENDPOINT

Descriptive statistics will be used to describe the effectiveness measures.

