2.1 Primary Objective

The primary safety objective of the study is to demonstrate the long-term safety of the Eversense CGM System.

The primary effectiveness objective of the study to demonstrate the long-term effectiveness of the Eversense CGM System.

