5.1.1 Descriptive Statistics

Continuous data will be summarized with mean, standard deviation, median, minimum, maximum, and number of evaluable observations. Categorical variables will be summarized with frequency counts and percentages. Confidence intervals may be presented, where appropriate, using the t-distribution for continuous data and Clopper-Pearson Exact method for categorical variables.

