5.6.2.1 Primary Analysis

Effectiveness will be measured as percentage change in the percent time in range (based on hours) at one month post-first sensor insertion compared to 12 months post-first sensor insertion using a time in range definition of glucose values between 70 mg/dL and 180 mg/dL. The Time in Range will be summarized as the mean of the subject percentages, together with the median, standard deviation, minimum, maximum, and 25th / 75th percentiles.

Summary statistics will also be provided for the change in HbA1c levels from baseline, and average hours of use per day.

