5.6.4 Additional Effectiveness Endpoints

There are no formal hypotheses or tests for statistical significance associated with additional effectiveness endpoints. Analyses will be based on the general methods outlined in this SAP. The following additional endpoints will be summarized with descriptive statistics.

- Average hours of use per day
- Change in HbA1c levels at each 6-month interval from baseline

Statistical Analysis Plan		Page 10 of 11
Sponsor	Study	Version
Senseonics	A Post Approval Study to Evaluate the Long-term Safety and Effectiveness of the Eversense® Continuous Glucose Monitoring (CGM) System	1.0

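### The effectiveness objective is to demonstrate, but the primary contrast (month 12 against month 1, both on-device, descriptive, no committed interval) can only describe whether time in range was maintained

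*Protocol*

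**What the plan says.** Protocol 3.5 states: "The primary effectiveness objective is to demonstrate the long-term effectiveness of the Eversense CGM System". SAP 2.1 repeats the objective.

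Protocol 3.6 defines the primary effectiveness endpoint as time in range (70 to 180 mg/dL) "at 12 months post-first Sensor insertion compared to the first month post-first Sensor insertion". SAP 5.6.2 gives the same contrast.

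Protocol 8.3 gives the measure: "Effectiveness will be measured as percentage change in the percent time in range (based on hours) at one month compared to 12 months". SAP 5.6.2.1 follows it and adds: "The Time in Range will be summarized as the mean of the subject percentages, together with the median, standard deviation", with the range and quartiles. Protocol 8.4.2, the effectiveness part of the sample size section, says only: "Descriptive statistics will be used to describe the effectiveness measures".

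On precision, the general rule in SAP 5.1.1 is: "Confidence intervals may be presented, where appropriate", using the t-distribution for continuous data. Nothing ties an interval to this endpoint.

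HbA1c is drawn at Visit 1 and every 6 months (Protocol 5.3). Its change from baseline is summarised directly after time in range in Protocol 8.3 and SAP 5.6.2.1, and SAP 5.6.4 lists it again: "Change in HbA1c levels at each 6-month interval from baseline".

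**The concern.** The safety objective uses the same verb, and it comes with null and alternative hypotheses, a 4% performance goal, a one-sided 0.05 exact test and a power statement. The effectiveness objective comes with a list of summary statistics. No outcome is named that would count against it.

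The contrast also has no pre-device reference. If the final report shows similar time in range in the two months, the stated objective invites the conclusion that effectiveness has been demonstrated, when the result says only that time in range did not move much while subjects used the system. Without an interval for the within-subject change, the report might not even make clear whether maintenance was shown or the estimate was too imprecise to say.

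**Working it through.** The documents give no effectiveness sample size, power, margin, SD or expected change, so there is no figure of the plan's own to reproduce. The check is of what the contrast can identify, and then of the precision that an interval could offer.

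**1. Is there a decision rule?** Protocol 8.2 (primary endpoints) contains only the safety endpoint; effectiveness is analysed under 8.3 (other endpoints). Protocol 8.4.2 and SAP 5.6.2.1 are descriptive. The per-protocol analysis in SAP 5.6.2.2 sets no criterion. The p<0.15 screens for site (SAP 5.7) and subgroup (SAP 5.9) only prompt exploration. No rule exists, so no probability of meeting the objective can be calculated.

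**2. Are both periods on-device?** Yes. Both are counted from first insertion (Protocol 3.6). Glucose values begin only after a 24-hour warm-up and the second calibration (Protocol 1.1.2). Users of other CGM systems are excluded (Protocol 4.2) and Visit 1 includes no CGM run-in, so the study holds no pre-device time in range.

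**3. What does the contrast identify?** Let B be a subject's pre-device time in range, and g1 and g12 the device gains in months 1 and 12. Leaving aside changes unrelated to the device:

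- month 1 = B + g1
- month 12 = B + g12
- contrast = (B + g12) − (B + g1) = g12 − g1

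If the gain is complete in month 1 and kept, g12 = g1 and the contrast is 0, whether the gain is 0, 5 or 10 points. If the gain builds up gradually the contrast is positive; if use or performance wanes it is negative. The contrast carries information on durability and none on the level of benefit.

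**4. Is the scale clear?** A move from 40% to 45% and one from 70% to 75% are both +5 points. As percentage changes they are 5/40 = +12.5% and 5/70 = +7.1%. The wording in Protocol 8.3 also puts one month first and 12 months second, so the sign is not fixed.

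**5. What precision could an interval have?** The 95% half-width is t(0.975, n−1) × SD/√n, where SD is that of the within-subject change. At least 273 subjects are to be inserted (Protocol 8.4.3), and missing data are not imputed (SAP 5.3), so the number of pairs will be 273 less those without usable data in both months. The documents do not give the number of pairs or the SD. The values below are assumptions, with 137 being about half of 273.

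| Pairs | SD of change (points) | Half-width (points) |
|---|---|---|
| 273 | 10 | about 1.2 |
| 137 | 15 | about 2.5 |

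A wider assumed range, 100 to 273 pairs with SD 8 to 15, gives 0.95 to 2.98 points.

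**6. Could a reader rebuild the interval from the planned tables?** Only if the mean, SD and n are given for the change itself. If only the two monthly summaries are tabulated, the SD of the change is √(s1² + s12² − 2·r·s1·s12), which needs the within-subject correlation r. SAP 5.6.2.1 names the change as the measure but says that time in range is what will be summarised, so the text does not settle this.

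**The case against.** The best defence is that this is a post-approval study with openly descriptive effectiveness measures. The objective concerns long-term effectiveness, and Protocol 2 presents the study as adding data on repeated use to premarket studies that ran to 90 and 180 days. Month 12 against month 1 is a sensible durability contrast. This stands: a descriptive endpoint is legitimate and need not be replaced. It does not explain why the objective is to demonstrate.

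A reader might also be tempted by stronger readings that the documents do not support:

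- *That no change is to be expected whether or not the system works.* Neither document states an expectation. It holds when the gain is constant from month 1, including a gain of zero; learning or waning could move time in range either way.
- *That intervals are ruled out.* SAP 5.1.1 allows them, and SAP 5.1.1 and 5.3 promise the number of evaluable observations. If mean, SD and n are tabulated for the change, the interval can be computed. The gap is that none is prespecified.
- *That HbA1c is kept apart as a minor endpoint.* Its change from baseline already sits with time in range in Protocol 8.3 and within the primary effectiveness analysis in SAP 5.6.2.1. Only the interval and the caveat are missing.
- *That a false-success rate can be attached to the plan.* That would require a rule, such as a month-12 mean no lower than month 1, and neither document states one.
- *That the final report will overclaim.* Neither document says which result would meet the objective, so this is a risk created by the wording and not a fault already shown.

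**Conclusion.** The point holds as a mismatch between objective and analysis. Followed as written, the plan yields summary statistics for a contrast between two on-device months. These can describe whether time in range was maintained from month 1 to month 12, but cannot demonstrate effectiveness against a pre-device state, and a null change would not distinguish a sustained early benefit from none. This part rests on the text alone.

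The size is a matter of what may be concluded; there is no error rate to quote. The half-width of about 1.2 to 2.5 points depends on the assumed number of pairs and SD. It shows only that a statement on maintenance is likely to be informative with the planned enrolment. The change is worth making because it alters the permissible conclusion and uses data already being collected. It does not call the design into question.

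**What to change.** 1. In SAP 5.6.2.1 and Protocol 8.3, replace the percentage change with the mean within-subject difference in time in range, month 12 minus month 1, in percentage points, with a two-sided 95% t interval and the number of pairs. This is a deliberate change of scale and should be recorded as such; it also fixes the direction. The months compared stay the same.
2. In Protocol 3.5 (and the matching synopsis row) and SAP 2.1, change *demonstrate* to *describe*. Alternatively, state there that the result supports only a conclusion on whether time in range was maintained from month 1 to month 12, with the lower confidence limit quoted in that conclusion.
3. In SAP 5.6.2.1 and 5.6.4, report the already planned within-subject HbA1c change from baseline to 12 months with its 95% interval, and state that it is an uncontrolled before-after change.

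The cost is an amendment to the wording of both documents and two intervals. No visit, sample or endpoint is added. The sponsor gives up the broader claim for a narrower one, and accepts that the interval may include a decline. No margin is proposed, and no pre-device time in range can be recovered, since none is collected.
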